### *Provider Assessment Surveys*

Inclusion criteria for the surveys are as follows: adult (18 years and over); clinicians employed by independent primary care practice that are members of HealthFirst's network and have enrolled into the study.

Exclusion criteria include the following: clinicians who are unable to complete the survey in the English language.

### *Key Informant Interviews*

Inclusion criteria for the interviews are as follows: Adult (18 years and over); must be a provider, clinic manager, Healthfirst staff, community advisory board member, research staff, or community health worker.

Exclusion criteria include the following: participants who are unable to participate in the interview conducted in the English language.

## **III. METHODS and PROCEDURES**

### **A. Methods and Procedures**

#### A1. Integrated EHR-CHW Intervention

### *Clinic Enrollment*

Practices that express interest in participating in the CHW intervention will sign a Memorandum of Understanding (MOU) that outlines the nature of the evaluation and the uses of any data collected, including:

- i. Training requirements
- ii. CHW intervention components to be implemented
- iii. Individual-level participant data to be extracted routinely from EHR and provided to study team
- iv. Confidentiality and data storage procedures

All relevant parties will then sign the MOU.

### *Intervention Components*

A minimum set of proposed intervention components will be implemented at all participating practices, including:

- An alert to identify South Asian patients with uncontrolled diabetes with HbA1c of >7
- 5 group-based health education sessions on diabetes management
- Provision of culturally and linguistically tailored health information and resources
- Two one-on-one in-person meetings and upto 9 follow-up calls/meetings to engage in goal-setting activities regarding changes to health behaviors, medication adherence, or other issues related to diabetes prevention as identified jointly by patient and CHW.
- Participants will develop with the CHW and receive a copy of their long-term and short-term Participant Action Plan.
- Referrals to other services available in the community (i.e. exercise classes, social services, mental health, tobacco cessation, etc.
- EHR-CHW integration supporting team-based care and feedback between PCPs and CHWs within the clinic, including:
  - First, providers will be sent Enrollment Update Letters during the recruitment phase of the intervention regarding the status of enrollment at their site (see Provider Enrollment Update Letter). This document will be sent as a password protected file with the password sent in a separate file from the enrollment status.
  - Second, templates will be created that CHWs can complete and upload into the EHR. Providers will be able to access these templates which will include the following: 1) CHW action planning documents and individualized counseling conducted during protocolized phone calls; and 2) Patient progress in reaching goals related to weight loss and behavior change.
  - Third, health coaching and referral materials will be made available to providers through the EHR, including 1) Culturally adapted CHW curriculum materials; and 2) Systems to link patient to community resources and activities.
  - Fourth, CHW communication with the healthcare team will be facilitated by participation and report-backs from CHWs during regular team “huddles” or staff meetings at least once per month. Further frequency of participation will be clinic-specific and guided by input from the provider and workflow analysis findings in order to avoid provider burn-out. CHWs will note any diabetes related events (high or low blood sugar events if encountered and communicated to the CHW), these will be noted in Encounter Reports.

### *CHW Curriculum*

Participants enrolled in the CHW intervention will receive group-based health education sessions:

Curriculum Session Title & Content	Tailored cultural components
Session 1: Diabetes Overview • Diabetes information	• Concept of prevention tied to South Asian core values (in religion/culture)

 
• Myths and Facts about diabetes
 
• Signs of Symptoms of Diabetes
 
• Goal-setting
 
• Blood Glucose Levels
 
• Basics on Eating Healthy
 
• Staying motivated and goal-setting
 
	
 
• Discussion of diabetes prevalence and increased risk of diabetes in Asians
 
• Discussion of diabetes among South Asians
 
• Explanation of BMI and at-risk BMI in Asian communities
 
• Dispelling common cultural misconceptions regarding diabetes (eg. getting diabetes is a natural part of aging)
 
• Incorporation of culturally appropriate images and language
 
• Discussion of diabetes complications, heart disease, stroke
 
• Discussion of prevention and inter-connectedness of chronic diseases
 
• Discussion of cholesterol and fats in diet, blood pressure and salt in diet
 
• Review of popular Punjabi foods high in salt and fat and limiting these foods
 
• Incorporation of culturally appropriate images/language
 


Session 2: Healthy Eating
 
 
• Nutrition and Food
 
• Eating a balanced diet: The Plate Method
 
• Overcoming barriers to eating out/social situations
 
• Reading a Nutrition Label
 
• Goal-setting for healthy eating
 
	
 
• Photos of typical South Asian foods
 
• Healthy elements in traditional South Asian cooking (eg. whole grain options for rotis, incorporating fruits and vegetables)
 
• Identifying and limiting deep-fried snacks high in salt and sweets high in fat and sugar; substituting sweets with fruits
 
• Healthy vegetarian options
 
• Healthy versions of popular South Asian recipes
 
• Following the Plate Method with traditional South Asian foods
 
• Managing expectations for eating out, langar at gurdwara (for Sikhs), etc.
 
• Reading food labels
 
• Working with women participants to improve nutrition in the entire household
 
• Incorporation of culturally appropriate images and language
 

Session 3: Physical Activity
 
 
• Caloric intake and energy balance
 
• Benefits and types of exercise
 
• Injury prevention
 
• Incorporating routines
 
• Overcoming barriers
 
• Practice activity and goal-setting
 
	
 
• Discussion of physical activity as essential to physical and mental fitness (eg. encouragement to practice similar discipline in physical activity as in prayer)
 
• Home-based exercise/activities
 
• Practice Activity
 
• Incorporation of culturally appropriate images and language
 

Session 4: Diabetes Management
 
 
• Diabetes complications
 
• Heart disease and stroke
 
• Communicating with the doctor
 
• Preparing for a doctor's visit
 
• Heart disease and stroke
 
• Staying motivated and goal-setting
 
• Discussion of diabetes complications, heart disease, stroke
 
• Discussion of prevention and inter-connectedness of chronic disease
 
• Discussion of cholesterol and fats in diet, blood pressure and salt in diet
 
	
 
• Incorporation of culturally appropriate images
 


Session 5: Stress and family support
 
 
• Effects of stress on health
 
• Stress and anger management
 
• Strategies to manage depression
 
 
Family support and goal-setting
	
 
• Discussion of meditation practice
 
• Progressive muscle relaxation for stress relief
 
• Strategies to manage depression; discussion around stigma associated with mental health (eg. depression)
 
• Incorporation of culturally appropriate images and language
 

--	---

## A2. Data Collection

### *EHR Data*

Data will be extracted from the PCP clinics' EHR systems every 6 months. De-identified EHR data will be collected from both treatment and control participants.

The process for collecting de-identified patient data is described here: This will entail PCP staff exporting de-identified patient information via a secure sftp site to a central repository managed by NYU. In order to de-identify patient information, PCP staff will generate a set of unique study identifiers to assign to treatment and control patients by associating a specific study number with a specific medical record number in the EHR system. The table of study identifiers and corresponding medical record numbers for the duration of the study in a secure and locked location in their respective clinics. All other potentially identifying data will also be stripped from the dataset prior to extraction. Only the PCPs will retain the table necessary to link patient identifiers and the study ID. Using this method, we will ensure that patient confidentiality is maintained, but that patients who are observed more than once will have the same study ID in each extraction, which is necessary for the planned analyses. Using the described approach, a pre-defined set of patient data will be exported every 6 months from the clinics' EHR systems into a de-identified Excel spreadsheet or delimited text file. Data elements will be based on functionalities of EHR platforms and will include patient demographic information such as year of birth, gender, race/ethnicity, diagnoses, medications, and laboratory results.

Follow-up height, weight and HbA1c measures will be obtained during routine office visit at six months. Scheduled office visits will be tracked via quarterly data pulls from the PCPs. If no visit is scheduled during the follow-up period, project CHWs will conduct follow-up calls to schedule patients for a height and weight recording at the clinic. Patient travel incentives will be provided to facilitate follow-up data collection.

De-identified EHR data will include the following:

- Clinic ID, patient study ID, and demographics - gender, age, race/ethnicity (if available), Language (if available)
  - Any diagnoses for: hypertension, diabetes, pre-diabetes, and high cholesterol during the study period , including month and year of diagnosis
  - Height and weight data during the data collection period, Month and year of measurement
  - All lab results for: HbA1c, lipid profile during the study period, Month and year of measurement

All data collection measures and procedures will be the same for treatment participants as control patients with the exception that data will no longer be de-identified. PHI and other data will be collected from treatment participants and with their full consent only. Treatment participants will also have the option to authorize staff to take photographs, video and audio for the purpose of disseminating health promotion and CHW led health intervention work in the audio/video consent form.

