## *2. Data collection and consenting with waitlisted control participants*

The NYU study team will only be collecting de-identified EHR data with control participants (n=443). EHR data will include clinical measures related to diabetes (e.g., HbA1c, BMI) and will be obtained from regularly generated diabetes registry lists that practices generate as part of quality improvement initiatives and these measures will be tracked over time. The PCPs will be conducting the de-identification and the link to the unique identifier will remain with the PCP staff. NYU study team members will not have access to these links. Beyond EHR data collection, no other data collection will occur with control participants (e.g., no survey data collection) and the control group will not have any interaction with study personnel for the purposes of research. PCPs will invite control participants to CHW education sessions at a later time (post round 1 of CHW intervention with treatment participants) as a point of service (i.e., not for research

purposes). The PCPs themselves are not involved in the research aside from providing NYU with de-identified EHR data.

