#### *Control Participants*

The NYU study team will only be collecting de-identified EHR data with control participants. The PCPs will be conducting the de-identification and the link to the unique identifier will remain with the PCP staff. NYU study team members will not have access to these links. Beyond EHR data collection, no other data collection will occur with control participants (e.g., no survey data collection) and the control group will not have any interaction with study personnel for the purposes of research. PCPs will invite control participants to CHW education sessions as a point of service (i.e., not for research purposes). For these reasons, we will not be obtaining consent with control participants.

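### The primary outcome fixes no single follow-up HbA1c and does not say how an untested patient is scored, so it depends on how often each arm is tested; passages on who is prompted for follow-up also conflict

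*Combined protocol and SAP*

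**What the plan says.** **Outcome.** The model in III.B1 (Aim 1 Analysis) sets Y = 1 for a drop of 0.5% or more within six months of the index visit, and Y = 0 for everyone else. The hypothesis in the same section speaks of the value six months after that visit and uses a strict threshold (more than 0.5%). III.A2 (EHR Data) states: "Follow-up height, weight and HbA1c measures will be obtained during routine office visit at six months". The extract, however, takes "All lab results for: HbA1c, lipid profile during the study period, Month and year of measurement". No rule selects among several results and no window is given. The eligibility criteria accept any reading above 7 in the previous 12 months, so the baseline value is not fixed either.

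**Missing data.** III.B1 expects none, because the data are administrative, and gives multiple imputation under MAR as a fallback. The Power Calculation assumes 15% loss. The Sampling paragraph assumes about 90% followed up at six months in both arms. VI.H leaves HbA1c testing to standard of care.

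**Prompting.** For patients with no scheduled visit, "project CHWs will conduct follow-up calls to schedule patients for a height and weight recording at the clinic". The plan adds: "Patient travel incentives will be provided to facilitate follow-up data collection". Neither sentence names an arm. The same section says: "All data collection measures and procedures will be the same for treatment participants as control patients". For controls, I.C2 says "the control group will not have any interaction with study personnel for the purposes of research" and, on the identity links held by practice staff, "NYU study team members will not have access to these links". VI.G adds: "For these reasons, we will not be obtaining consent with control participants".

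**The concern.** Followed to the letter, the coding rule does three things. It counts any early qualifying value among all those extracted. It excludes a six-month visit that falls a little late. It scores a person with no follow-up HbA1c as a failure, although the same section prescribes imputation for missing data. Each of these ties the outcome to how often, and when, a patient is tested in routine care.

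That matters if testing differs between arms, and some contact is treatment-only. The calls and travel incentives cannot reach controls without breaching the no-contact and no-consent statements. Only treatment patients get up to 9 CHW follow-up calls and a session that covers communicating with the doctor. If untested patients score 0, the arm tested more gains a false advantage. If they are imputed, the arm with more readings still has more chances to show one qualifying value. Separately, two analysts working from the same extract could build different primary outcomes and both claim to have followed the plan.

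**Working it through.** **Inputs from the documents:** 443 per arm, two-sided 0.05, a 10-point difference in responders, 15% loss. **Assumed, because the documents give no figure:** responder rates of 20-50%, testing shares by arm, the share with a second reading, and the correlation between readings. Clinic clustering is ignored; randomisation is individual within PCP.

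**Formula.** For observed rates p1 and p2, let d = p1 - p2 and let p̄ be their mean. Then s0 = √[2p̄(1-p̄)/n], s1 = √{[p1(1-p1)+p2(1-p2)]/n} and c = 1.96·s0. The rejection probability is 1-Φ((c-d)/s1) + Φ((-c-d)/s1).

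**Step 1. The plan's own power.** 443 × 0.85 = 376 evaluable per arm. At control rates of 20, 30, 35, 40 and 50%, power for 10 points is 88.8, 82.1, 80.0, 78.8 and 78.8%. The stated figure of more than 80% therefore reproduces to within about 2 points. It assumes equal loss in both arms.

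**Step 2. No true effect, untested scored 0, n = 443.** The false difference is the responder rate times the testing gap.

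| Responder rate | 90% v 88% tested: difference, rejection | 90% v 85% tested: difference, rejection |
|---|---|---|
| 20% | 0.4 points, 5.3% | 1.0 points, 6.8% |
| 30% | 0.6, 5.5% | 1.5, 8.0% |
| 40% | 0.8, 5.7% | 2.0, 9.6% |
| 50% | 1.0, 6.0% | 2.5, 11.6% |

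Example, last cell: p1 = 0.5 × 0.90 = 0.450 and p2 = 0.5 × 0.85 = 0.425, so d = 0.025. s0 = 0.0333, c = 0.0653 and s1 = 0.0333. The two tails are about 0.113 and 0.003, together 11.6%.

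**Step 3. The same eight cases, untested treated as missing, MAR within arm.** Simulated rejection using observed cases only is 5.0-5.1%.

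**Step 4. No true effect, any qualifying reading counts.** With two equally distributed readings, P(either qualifies) = 2p - P(both), so a second reading adds p - P(both). With bivariate normal changes:

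| p | Correlation 0.5 | 0.7 | 0.9 |
|---|---|---|---|
| 20% | 11.3 points | 8.7 | 5.0 |
| 30% | 14.3 | 10.9 | 6.2 |
| 40% | 16.1 | 12.2 | 6.9 |
| 50% | 16.7 | 12.7 | 7.2 |

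If 40% v 30% of patients have a second reading, the false difference is 0.1 × gain = 0.5-1.7 points. Rejection at 376 per arm is 5.3-7.5%.

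**Step 5. Equal 85% testing, true 10-point effect.** Scoring untested as 0 shrinks the difference to 0.85 × 10 = 8.5 points, with n = 443.

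| Control rate | All 443 tested | 376 evaluable | Untested = 0 | Cost against 376 |
|---|---|---|---|---|
| 20% | 93.2% | 88.8% | 87.3% | 1.5 points |
| 30% | 87.8% | 82.1% | 79.1% | 3.0 |
| 40% | 85.0% | 78.8% | 74.1% | 4.7 |
| 50% | 85.0% | 78.8% | 71.8% | 7.0 |

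This step needs no testing gap. It shows a power cost, not bias between arms.

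**Step 6. The prompting passages side by side.** If project CHWs call controls, the no-contact statement fails, and the study team holds no link with which to identify them. If they call only treatment patients, the statement of equal procedures fails. The documents offer no third route.

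**The case against.** Most of the case against bias stands.

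- **The calls name only height and weight.** That a prompted visit also yields an HbA1c is an inference. It is plausible, since the plan obtains all three at the same visit, but it is not written. The CHW follow-up calls are described as dealing with diet and physical activity, not testing.
- **Some features could narrow a gap.** The alert and registry are set up clinic-wide, patients are randomised within PCP, and the Sampling paragraph plans 90% follow-up in both arms.
- **Untested = 0 is the weaker reading.** The imputation clause in the same section would have little to act on if every untested patient were already scored. Under imputation with MAR within arm, Step 3 leaves no inflation.
- **The intended reading can be guessed.** The hypothesis and the EHR Data section both point to six months, and the list of all laboratory results is an extraction list, not an endpoint rule. But the model's coding says something different, and nothing states which governs.
- **The 15% may simply be a cautious allowance.** It still does not fit the expectation of no missing data, or the 90%.

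A reader might infer that the plan prompts HbA1c testing in one arm only and so biases the primary result. The documents do not support that: they show a possible cause, but neither an HbA1c prompt nor a gap in testing.

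**Conclusion.** The point holds as a defect of definition that should be fixed. The coding rule, the hypothesis and the EHR Data section describe different outcomes; no rule selects a reading; the status of an untested patient is left open; and the passages on prompting cannot all be followed.

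The effect on the type I error is illustrative only. It is about 5-7% if any reading counts (40% v 30% retested), 5-12% if untested patients score 0 with a 2-5 point testing gap, and about 5% if they are treated as missing and MAR holds within arm. All three rest on assumed responder rates of 20-50%. Larger gaps would give far larger figures, but nothing in the documents supports assuming them, and these numbers should not set the severity. The power cost of scoring 0, 1.5-7 points beyond the planned loss at 85% testing, needs no gap. It does need the literal reading of the coding rule.

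**What to change.** 1. Derive the outcome from one follow-up HbA1c per person: the value closest to six months after a defined index date, in one window identical in both arms, with a tie rule. Set the window in calendar months, since only month and year are extracted. End it before the second-round sessions are offered to controls.
2. Name the single baseline HbA1c from which the change is measured, and use one threshold throughout (0.5% or more, or strictly more).
3. State that no HbA1c in the window is missing, not 0. Impute by arm using baseline HbA1c, with non-responder and tipping-point sensitivity analyses.
4. Report by arm the share tested in the window and the number of HbA1c tests per person.
5. Replace the sentence that expects no missing data, and reconcile it with the 15% loss and the 90% follow-up.
6. Reconcile the EHR Data section with the two sections on controls: who is prompted, and who receives travel incentives. Logging prompted visits is useful description but does not make the arms comparable, because coaching may itself raise visit rates.

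**Cost.** Mostly SAP wording, a log and a few analyses. It is not free: readings outside the window no longer count, so missingness may rise. If it went from 15% to 25% (an assumption; 443 × 0.75 = 332 per arm), complete-case power for 10 points would fall from 79-89% to 74-85% at control rates of 20-50%. Any new contact with controls would need ethics review, because they are not consented.

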## B. Data Analysis and Data Monitoring

### B1. Aim 1 Analysis

AIM 1: Specific Aim I: Test the effectiveness of a multi-level diabetes management intervention compared to usual care. The primary outcome is reduction in HbA1c for patients with baseline HbA1c of >7%. The secondary outcomes include enhanced use of community and social services and increased self-efficacy.

*Hypothesis:* Individuals receiving the multi-level diabetes management intervention will be more likely to achieve >0.5% reduction in HbA1c 6 months following the index office visit than individuals receiving care as usual.

The analysis of the effect of intervention on the outcome measure will proceed using a Generalized Linear Mixed Model (GLMM). In particular, we will use a random effects model that assumes a binomial distribution with a logit link function. The comparison will make no linear assumption about the time trend for each outcome over the course of the trial. The model will be as follows:

$$(1) \quad \text{logit}(Y_{ijt}) = \mu + \alpha_j + \theta_t + \tau C_i,$$

where  $Y_{ijt} = 1$  if the  $i^{\text{th}}$  subject attached to the  $j^{\text{th}}$  clinic at time quarter  $t$  achieves an HbA1c reduction of 0.5% or more within six months following the index visit,  $Y_{ijt} = 0$  otherwise.  $\alpha_j$  is a random effect for clinic  $j$  with mean 0 and variance  $\sigma^2_b$ .  $\theta_t$  is a time-specific effect of quarter  $t, t \in (1, 2, \dots, 12)$ .  $C_i$  is an indicator variable, and  $C_i = 1$  if individual  $i$  receives care under the EHR/CHW intervention,  $C_i = 0$  if individual  $i$ .  $\tau$  represents the treatment effect of the intervention. The model will be fit using the LME4 package using R software. The hypothesis will be tested using two-sided level of significance  $\alpha = .05$ . Because outcome data will be derived from administrative data, we do not anticipate missing data. However, in the event that there is missing data, we will use multiple imputation under the assumption of data missing at random (MAR). This is consistent with following an intent-to-treat protocol. Sex as a biological variable will be addressed by exploring gender as a potential moderator of intervention effects.

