## I. PURPOSE OF THE STUDY AND BACKGROUND

### A. Purpose of the Study

The proposed study “Integrated Community-Clinical Linkage Model to Manage Diabetes among South Asians” aims to test the effectiveness of a multi-level diabetes management intervention compared to usual care. The primary outcome is reduction in hemoglobin A1c (HbA1c) for patients with baseline HbA1c of  $>7\%$ . The secondary outcomes include enhanced use of community and social services and increased self-efficacy.

The integrated intervention involves:

1. An electronic health record (EHR) intervention for primary care providers (PCPs) utilizing embedded alerts to identify South Asian patients with uncontrolled diabetes.
2. Registry-driven community health worker (CHW)-led health coaching for patients. Using a stepped-wedge design, we will implement the study in 20 NYC PCP clinics enrolling 886 South Asian patients at- risk for Type 2 Diabetes Mellitus (T2DM).
3. Linkage to culturally relevant community-level resources
4. CHW-integration into primary care teams. The project will leverage Health Information Technology (HIT) tools to support integration of CHWs in healthcare teams, feedback between healthcare providers and CHWs, and establish a referral mechanism between CHWs, patients, and community resources

In addition, using a mixed-methods approach and the RE-AIM evaluation framework, we aim to systematically assess the implementation process and delineate factors that influence adoption, sustainability, and scalability of the integrated EHR-CHW intervention within applied practice settings.

This will be achieved through the completion of:

5. Provider Surveys (n=80) to capture data on satisfaction with workflow before and after intervention, information sources for EHR-CHW initiatives before and after intervention, acceptability of and satisfaction with the integrated EHR-CHW intervention, and barriers and facilitators of point-of-care use of the tools.

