### C. Study Design

#### C1. Overall Design/Clinic Selection/Clinic Enrollment

We will use a randomized controlled trial design with staggered-entry and a waitlisted control group to compare the effectiveness of an alert and registry-driven CHW-led coaching compared with usual care among patients with HbA1c at  $>7\%$ . Randomization will be at the individual-level and stratified by PCP, meaning eligible treatment and control participants will be randomized for each PCP. PCPs will be clustered into waves, aligning with the original stepped-wedge design. Entry into the study will be staggered in three waves, with each wave consisting of six to seven PCPs (See Figure 1). All 20 PCPs will be recruited and enrolled by month 6 of Year 1 (study period 6, Figure 1), and we will assign 6-7 practices into each of the 3 waves upon enrollment. For each PCP, there will be a total of two rounds of consecutive six-month CHW intervention periods for the treatment group: 1 month for recruitment and enrollment of treatment participants and five months of community health worker-led group education sessions (approximately one session per month). Data related to the study outcomes will be extracted from EHR systems a total four times (baseline, 6 month, 12 month, and 18 month) for each PCP; we will be comparing EHR data from 443 treatment participants with 443 control participants. Prior to allocation into treatment group, each treatment participant will be matched to a control participant based on age, gender, and BMI. Treatment participants will be split into two groups and assigned to either first or second round. All control participants will be waitlisted during the first round and will be offered the full CHW group education sessions during the second round as a point of service (i.e., not for research purposes).

Randomization at each PCP will occur during the first round. PCPs will be placed into waves based on geographic location and CHW caseload considerations. PCPs will be eligible for participation if they have a) an overall patient volume of  $N \geq 1000$  ; b) at least 70% of the patient population is South Asian; and c) the practice has used EHR for at least 12 months. All PCPs will sign a Memorandum of Understanding (MOU) between the PCP and NYU outlining study commitments.

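### Aim 1 claims the effect of the multi-level EHR/CHW intervention against usual care, but randomising patients within EHR-enabled practices can estimate only the CHW-delivered part, and neither secondary outcome has a described control-arm source

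*Combined protocol and SAP*

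**What the plan says.** **The claim.** Section I.A says the study "aims to test the effectiveness of a multi-level diabetes management intervention compared to usual care" and lists an EHR intervention for providers as the first of four components. Section III.B1 repeats the aim ("Test the effectiveness of a multi-level diabetes management intervention compared to usual care"), and its hypothesis is that treated patients will more often reach the HbA1c target "than individuals receiving care as usual". In model (1) the indicator C_i equals 1 if the individual "receives care under the EHR/CHW intervention", and tau "represents the treatment effect of the intervention". Section I.C1 uses a narrower description, to "compare the effectiveness of an alert and registry-driven CHW-led coaching compared with usual care", but still sets it against usual care.

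**The allocation.** Section I.C1: "Randomization will be at the individual-level and stratified by PCP, meaning eligible treatment and control participants will be randomized for each PCP". Treatment participants are divided between two consecutive six-month rounds. Controls wait through round 1 and are offered the group sessions in round 2.

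**Where the EHR component goes.** Section I.C2 makes the EHR changes at each study clinic and trains its providers and staff, with about 8 hours of training for clinicians. Section I.C3 makes coaching and referral materials, and systems for linking patients to community resources, available to providers through the EHR.

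**Secondary outcomes.** Section III.B1: "The secondary outcomes include enhanced use of community and social services and increased self-efficacy". The part of Section I.C2 on waitlisted controls, and Section VI.G, limit control data to the de-identified EHR extract. The first of these adds that controls complete no survey.

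**The concern.** A component that both arms receive cannot contribute to the difference between them. If the EHR changes and clinician training reach a practice as a whole, a control there is not receiving care as it was before the study. A positive tau would then be reported as evidence for the four-component package when it speaks only to the CHW-delivered part. A null tau would be reported as failure of the package when the EHR part was never tested. This matters because the stated purpose is a reproducible model for other healthcare and community settings.

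For the secondary outcomes, a change in self-efficacy or service use would appear under an aim that compares with usual care, although nothing was measured in the comparison group. Regression to the mean, secular change and survey effects could not be separated from the intervention.

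**Working it through.** **Step 1: what tau contains.** Model (1) is logit = μ + α_j + θ_t + τC_i, where α_j is the clinic effect and θ_t the quarter effect. Write the EHR effect in clinic j as ε·E_j, with E_j = 1 where the EHR component is present. By Section I.C2, E_j = 1 in all 20 clinics.

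- Treatment patient in clinic j: μ + α_j + θ_t + ε + τ
- Control patient in clinic j: μ + α_j + θ_t + ε
- Difference: τ

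The term ε cancels and is absorbed into μ. On the logit scale the package against care without the EHR changes would be ε + τ, where τ is the CHW effect given that the EHR component is present. Only τ is estimable. This holds for any value of ε, so no effect size is needed.

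**Step 2: could the staggered waves supply ε?** No. Section I.C1 places PCPs in waves by geography and CHW caseload, not at random. Model (1) has no term for when the EHR component went live.

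**Step 3: data sources for the secondary outcomes.**

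| Outcome | Treatment arm | Control arm |
|---|---|---|
| Self-efficacy | Survey at baseline and about six months (I.C2) | None: no survey (I.C2, VI.G) |
| Use of community and social services | No source is tied to this outcome; Healthfirst claims are named in the treatment consent (VI.G) | None described |

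The extract in Section III.A2 holds five groups of fields: identifiers and demographics, diagnoses, medications, height and weight, and laboratory results. None of the five holds either outcome. The data-warehouse files in the Aim 2 Analysis concern clinicians' use of the system, not patients' use of services. Described control-arm sources: 0 of 2.

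**Step 4: the stated sample size.** Section III.B1 gives 886 participants, 1:1, a 10-point difference, two-sided 0.05, more than 80% power and 15% loss. The control proportion is not stated. With the pooled-variance normal approximation and an assumed 35% v 45%, 80% power needs 376 per arm. Then 376 / 0.85 = 442.4, rounded up to 443, and 2 × 443 = 886. The plan's figure reproduces.

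**Step 5: power of a round-1 sensitivity analysis.** Assume equal rounds (no split is given) and apply the 15% loss. Treatment: 443 / 2 × 0.85 = 188. Control: 443 × 0.85 = 377. The difference is 10 points, and no design effect is applied because patients are randomised within PCP.

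| Assumed control proportion | All participants, 377 v 377 | Round 1 only, 188 v 377 |
|---|---|---|
| 20% | 89% | 75% |
| 30% | 82% | 66% |
| 40% | 79% | 62% |

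If 40% or 60% of treatment participants are in round 1 (151 or 226 v 377), power at a 30% control proportion is 60% or 71%.

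**The case against.** **This is only a label.** Section I.C1 already describes alert- and registry-driven CHW coaching, the alert is presented as a means of finding patients, and Aim 1 claims no separate EHR effect. It stands that the randomisation is sound and the CHW increment is estimable. But the Aim 1 text and the definition of C_i claim more than that, and even the narrower sentence keeps usual care as the comparator.

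**Controls may not be touched by the EHR component.** The list in Section III.A1 of components implemented at all practices also includes the group sessions, which controls do not get in round 1. Being on that list therefore does not show that a component reaches controls. This stands, and the argument rests instead on Sections I.C2 and I.C3. That the alert fires for controls is an inference. A reader might go on to infer that the contrast is diluted by some amount. The documents give no figure for that, and none is claimed.

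**Round 2.** A reader might infer that the primary comparison must be cut back to round 1. The documents do not support this. The hypothesis is set at 6 months, the analysis is described as intent-to-treat with 1:1 allocation, and Section I.C1 does not say that rounds are assigned at random. Controls are offered the group sessions, but no section offers them the individual calls or action plans, so the contrast narrows but does not vanish. Round 2 is a limitation to disclose.

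**The C_i = 0 phrase stops short.** A reader might infer that the model has no comparator. The break may come from the text conversion, and the hypothesis names care as usual.

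**Common procedures.** Section III.A2 says that data collection is the same in both arms apart from de-identification. That sentence sits under EHR data and does not override the explicit limits on control data in Sections I.C2 and VI.G. CHW encounter reports may capture referral requests, but they are described only for study participants in contact with a CHW.

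**Conclusion.** The concern holds as a mismatch between the stated estimand and the randomised contrast. With 0 of 20 planned practices lacking the EHR component, tau is a randomised estimate of the CHW-delivered components in EHR-enabled practices. It is not an estimate of the EHR component or of the whole package against usual care. Neither secondary outcome (0 of 2) can be compared with usual care.

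This rests on the EHR changes and training being practice-wide, which Sections I.C2 and I.C3 state, and on no section withholding them from controls. It does not rest on any assumed effect of the alert. It does not show that the HbA1c comparison is invalid or that 886 is too few: the sample size reproduces for the full randomised comparison. If the 10-point difference was meant as treatment against controls in EHR-enabled practices, the stated power is unchanged.

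**What to change.** 1. Restate Aim 1 (Sections I.A and III.B1), the hypothesis and the design sentence in Section I.C1 as allocation to CHW-delivered coaching and linkage against waitlist, both within practices that have the EHR component.
2. Define C_i by randomised allocation: 1 = CHW, 0 = waitlist.
3. State that the EHR component is not randomised, and limit the conclusion to match.
4. Report self-efficacy and service use as treatment-arm before-after descriptive outcomes with no usual-care claim, and name the data source for service use.
5. Keep the primary HbA1c comparison as randomised, with all participants. State that offering controls the group sessions in round 2, when some treatment participants also have theirs, may dilute it.
6. Add a sensitivity analysis of round-1 treatment participants against controls before the offer. Note its lower power (about 62 to 75% under the assumptions above) and that random assignment to rounds is not stated.

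**Cost.** Wording in three sections and one extra sensitivity analysis. Randomisation, recruitment, EHR extraction and the planned sample size do not change. The price is a narrower claim: the trial would give no estimate of the whole package, or of the EHR component, against usual care.
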